8.1 Definitions

Unanticipated Problems Involving Risk to Subjects or Others (UPIRTSO)

Any unanticipated problem or adverse event that meets the following three criteria:

- Serious: Serious problems or events that results in significant harm, (which may be physical, psychological, financial, social, economic, or legal) or increased risk for the subject or others (including individuals who are not research subjects). These include: (1) death; (2) life threatening adverse experience; (3) hospitalization - inpatient, new, or prolonged; (4) disability/incapacity - persistent or significant; (5) birth defect/anomaly; (6) breach of confidentiality and (7) other problems, events, or new information (i.e. publications, DSMB reports, interim findings, product labeling change) that in the opinion of the local investigator may adversely affect the rights, safety, or welfare of the subjects or others, or substantially compromise the research data, **AND**
- Unanticipated: (i.e. unexpected) problems or events are those that are not already described as potential risks in the protocol, consent document, not listed in the Investigator's Brochure, or not part of an underlying disease. A problem or event is "unanticipated" when it was unforeseeable at the time of its occurrence. A problem or event is "unanticipated" when it occurs at an increased frequency or at an increased severity than expected, **AND**
- Related: A problem or event is "related" if it is possibly related to the research procedures.

Adverse Event

An untoward or undesirable experience associated with the use of a medical product (i.e. drug, device, biologic) in a patient or research subject.

Serious Adverse Event

Adverse events are classified as serious or non-serious. Serious problems/events can be well defined and include;

- death
- life threatening adverse experience
- hospitalization
- inpatient, new, or prolonged; disability/incapacity
- persistent or significant disability or incapacity
- birth defect/anomaly

and/or per protocol may be problems/events that in the opinion of the sponsor-investigator may have adversely affected the rights, safety, or welfare of the subjects or others, or substantially compromised the research data.

All adverse events that do not meet any of the criteria for serious, should be regarded as **non-serious adverse events**.

Adverse Event Reporting Period

The study treatment follow-up period is defined as the end of the day 2 follow-up phone call for the study (1 day following the last administration of study treatment). This phone call concludes the Adverse Event Reporting Period.

Preexisting Condition

A preexisting condition is one that is present at the start of the study. A preexisting condition should be recorded as an adverse event if the frequency, intensity, or the character of the condition worsens during the study period.

General Physical Examination Findings

At screening, any clinically significant abnormality should be recorded as a preexisting condition. At the end of the study, any new clinically significant findings/abnormalities that meet the definition of an adverse event must also be recorded and documented as an adverse event.

Post-study Adverse Event

All unresolved adverse events should be followed by the sponsor-investigator until the events are resolved, the subject is lost to follow-up, or the adverse event is otherwise explained. At the last scheduled visit, the sponsor-investigator should instruct each subject to report, to the sponsor-

investigator, any subsequent event(s) that the subject, or the subject's personal physician, believes might reasonably be related to participation in this study.

Abnormal Laboratory Values

Laboratory values associated with this study will be a part of the patient's clinical medical record, and clinically indicated. No follow up laboratory values will be obtained following imaging.

Hospitalization, Prolonged Hospitalization or Surgery

Any adverse event that results in hospitalization or prolonged hospitalization should be documented and reported as a serious adverse event unless specifically instructed otherwise in this protocol. Any condition responsible for surgery should be documented as an adverse event if the condition meets the criteria for an adverse event.

Neither the condition, hospitalization, prolonged hospitalization, nor surgery are reported as an adverse event in the following circumstances:

- Hospitalization or prolonged hospitalization for diagnostic or elective surgical procedures for a preexisting condition. Surgery should **not** be reported as an outcome of an adverse event if the purpose of the surgery was elective or diagnostic and the outcome was uneventful.
- Hospitalization or prolonged hospitalization for therapy of the target disease of the study, unless it is a worsening or increase in frequency of hospital admissions as judged by the clinical investigator.

8.2 Recording of Adverse Events

At each contact with the subject, the study team must seek information on adverse events by specific questioning and, as appropriate, by examination. Information on all adverse events should be recorded immediately in the source document, and also in the appropriate adverse event section of the case report form (CRF) or in a separate adverse event worksheet. All clearly related signs, symptoms, and abnormal diagnostic, laboratory or procedure results should be recorded in the source document.

All adverse events occurring during the study period must be recorded. The clinical course of each event should be followed until resolution, stabilization, or until it has been ultimately determined that the study treatment or participation is not the probable cause. Serious adverse events that are still ongoing at the end of the study period must be followed up, to determine the final outcome. Any serious adverse event that occurs during the Adverse Event Reporting Period and is considered to be at least possibly related to the study treatment or study participation should be recorded and reported immediately.

8.3 Reporting of Serious Adverse Events and Unanticipated Problems

When an adverse event has been identified, the study team will take appropriated action necessary to protect the study participant and then complete the Study Adverse Event Worksheet and log. The sponsor-investigator will evaluate the event and determine the necessary follow-up and reporting required.

8.3.1 Sponsor-Investigator reporting: notifying the Mayo IRB

The sponsor-investigator will report to the Mayo IRB any UPIRTSOs and Non-UPIRTSOs according to the Mayo IRB Policy and Procedures.

The sponsor-investigator will review all adverse event reports to determine if specific reports need to be made to the IRB and FDA. The sponsor-investigator will sign and date the adverse event report when it is reviewed. For this protocol, only directly related SAEs/UIRTSOs will be reported to the IRB.

The relationship of an AE to the Investigational Drug is a clinical decision by the sponsor-investigator (PI) based on all available information at the time of the completion of the CRF and is graded as follows:

1. **Not related:** a reaction for which sufficient information exists to indicate that the etiology is unrelated to the study drug; the subject did not receive the study medication or the temporal sequence of the AE onset relative to administration of the study medication is not reasonable or the event is clearly related to other factors such as the subject's clinical state, therapeutic intervention or concomitant therapy.
2. **Unlikely:** a clinical event, including laboratory test abnormality, with a temporal relationship to drug administration which makes a causal relationship improbable and in which other drugs, chemicals, or underlying disease provide plausible explanations.
3. **Possible:** a clinical event, including laboratory test abnormality, with a reasonable time sequence to administration of the drug but which could also be explained by concurrent disease or other drugs or chemicals; information on drug withdrawals may be lacking are unclear.
4. **Probable:** a clinical event including laboratory test abnormality, with a reasonable time sequence to administration of the drug, unlikely to be attributed to concurrent disease or other drugs or chemicals and which follows a clinically reasonable response on withdrawal (de-challenge): re-challenge information is not required to fulfil this definition.
5. **Definite:** a reaction that follows a reasonable temporal sequence from administration of the drug, or in which the drug level has been established in body fluids or tissues, that follows a known or expected response pattern to the suspected drug, and that is confirmed by improvement on stopping or reducing the dosage of the drug, and reappearance of the reaction on repeated exposure (re-challenge).

The maximum intensity of an AE during a day should be graded according to the definitions below and recorded in details as indicated on the CRF. If the intensity of an AE changes over a number of days, then separate entries should be made having distinct onset dates.

1. Mild: AEs are usually transient, requiring no special treatment, and do not interfere with patient's daily activities.
2. Moderate: AEs typically introduce a low level of inconvenience or concern to the patient and may interfere with daily activities, but are usually ameliorated by simple therapeutic measures.
3. Severe: AEs interrupt a patient's usual daily activity and traditionally require systemic drug therapy or other treatment.

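### Section 8.3.1 sets two conflicting thresholds for reporting to the IRB, and the narrower one uses a term the protocol never defines

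*Combined protocol and SAP*

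**What the plan says.** All of the text is in section 8 of the combined protocol and SAP.

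- **8.1 Definitions.** A UPIRTSO must be serious, unanticipated and related. A problem meets the third condition "if it is possibly related to the research procedures".
- **8.2 Recording of Adverse Events.** All adverse events are recorded. A serious adverse event in the reporting period that "is considered to be at least possibly related to the study treatment or study participation should be recorded and reported immediately" is singled out. The section does not say to whom it is reported.
- **8.3.1, first sentence.** "The sponsor-investigator will report to the Mayo IRB any UPIRTSOs and Non-UPIRTSOs according to the Mayo IRB Policy and Procedures".
- **8.3.1, end of the second paragraph.** "For this protocol, only directly related SAEs/UIRTSOs will be reported to the IRB". I take the last acronym to be a typing slip for UPIRTSOs.
- **8.3.1, causality scale.** There are five grades: Not related, Unlikely, Possible, Probable and Definite. The scale rates the relation of an event to the investigational drug.
- **8.3.2.** Unexpected serious suspected adverse reactions go to the FDA within 7 or 15 calendar days. The *directly related* limit does not appear there.

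**The concern.** The study team needs one rule for what goes to the IRB, and 8.3.1 gives two. The first takes in every UPIRTSO, a category that by definition starts at possibly related. The second admits only events that are *directly related*. On an ordinary reading that is a higher bar, and the protocol does not say where it lies.

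The events between the two thresholds are plausible ones in this design. The Possible grade describes an event "with a reasonable time sequence to administration of the drug but which could also be explained by concurrent disease or other drugs or chemicals". Every subject has high-risk or very high-risk prostate cancer. In one imaging session he receives C-11 choline and gadobutrol, and also glucagon unless he has a history of diabetes (sections 3 and 3.3). A competing explanation is therefore close at hand for almost any reaction that day.

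The IRB's view also carries weight here. Section 3.6 expects no adverse reactions to the tracer, so a serious one would probably count as unanticipated. Section 8.4 declares stopping rules not applicable, and sections 8.5 and 8.5.1 make the Principal Investigator responsible for safety oversight.

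**Working it through.** There is no figure to reproduce and no arithmetic applies. The check is to set the passages side by side.

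**Step 1. Threshold, scope and recipient in each place**

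| Place | Relatedness threshold | Related to what | Recipient |
|---|---|---|---|
| 8.1 (definition) | possibly | research procedures | none; defines the category only |
| 8.2 | at least possibly | study treatment or participation | not named |
| 8.3.1, first sentence | the 8.1 threshold, for UPIRTSOs | as in 8.1 | IRB |
| 8.3.1, second paragraph | *directly* (undefined) | not stated | IRB |
| 8.3.2 | suspected reaction | study drug | FDA |

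**Step 2. Where the conflict lies.** Only the two sentences of 8.3.1 direct events to the IRB. Through 8.1, the first sentence includes a serious, unanticipated event that is possibly related. On a literal reading the second sentence excludes it. The conflict is therefore inside 8.3.1, with 8.1 supplying the meaning of the first sentence. Section 8.2 points the same way as 8.1, but it names no recipient and so contradicts the restriction only indirectly.

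**Step 3. What the restriction would hold back.** Three of the five grades correspond to possibly related or stronger: Possible, Probable and Definite. The protocol ties *directly related* to none of them, so the effect depends on the meaning chosen.

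| If *directly related* meant | Grades kept from the IRB | Remark |
|---|---|---|
| Definite only | Possible, Probable | Definite also calls for recurrence on re-exposure, and each subject receives one dose |
| Probable or Definite | Possible | |
| Possible or stronger | none of the three | the word *directly* would then add nothing |

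Possible events are lost under either meaning that gives *directly* any force. Probable events are lost under only one of them.

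**Step 4. Scope of the scale.** The five grades rate relation to the investigational drug. Section 8.1 speaks of research procedures, and 8.2 also covers participation. An event attributable to gadobutrol, glucagon or the MR examination could meet the 8.1 test and still be rated unrelated to C-11 choline. A threshold expressed only in these grades would not match 8.1.

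**The case against.** The strongest defence is that the first sentence of 8.3.1 defers to IRB policy and that this policy governs. The sponsor-investigator also reviews every adverse event report to decide what goes to the IRB and the FDA. The restrictive sentence might be meant only to limit expedited reports, and few events are likely with 20 subjects, one tracer dose and a reporting period that ends with the Day 2 call. Part of this stands: the number of affected events is probably small. The rest does not remove the conflict. The restrictive sentence says nothing about timing, names UPIRTSOs among the events it limits, and is worded as specific to this protocol, so staff could reasonably take it as an exception.

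A reader might also infer more than the text supports:

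- *Serious events graded Possible or Probable go unreported altogether.* They do not. Section 8.2 requires all adverse events to be recorded, and 8.3.2 keeps the FDA route for unexpected serious suspected drug reactions. The FDA is a different recipient, so that route does not replace IRB review, but the gap is limited to the IRB.
- *No event could ever qualify.* That holds only if *directly* means Definite, which the protocol nowhere says.
- *Sections 8.1 and 8.2 themselves require these events to go to the IRB.* Section 8.1 is a definition, and 8.2 names no recipient.
- *The restriction overrides IRB policy.* The protocol does not say which sentence takes precedence, and the policy is not among the documents.
- *Every possibly related serious event is affected in the same way.* A serious event that was anticipated is not a UPIRTSO. It would reach the IRB only through the Non-UPIRTSO clause, whose content depends on that policy.

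**Conclusion.** The point holds as an internal contradiction in a safety-reporting rule. Section 8.3.1 gives two IRB thresholds that cannot both be followed, and the narrower one rests on an undefined term. Taken literally, it withholds from the IRB serious, unanticipated events that are possibly related to the research procedures. It could withhold Probable events too, but the text does not settle that.

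This rests on two assumptions: that the misspelled acronym means UPIRTSOs, and that *directly* is meant to be stricter than *possibly*. The number of events affected cannot be estimated from the documents. The matter touches no endpoint, sample size, power statement or analysis. It should still be corrected, because the rule is operative and staff cannot apply it without guessing.

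**What to change.** Reconcile the passages in one of two ways:

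1. Delete the restrictive sentence from 8.3.1, so that the opening sentence and the 8.1 definition stand.
2. Restate it on the threshold already used in 8.1 and 8.2: at least possibly related to the research procedures, the study treatment or study participation.

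If the second route is taken, do not tie the threshold to the five-grade scale alone, since that scale is confined to the investigational drug and would leave out procedure-related events that 8.1 includes. In either case, use the same wording in 8.1, 8.2 and 8.3.1, and name the recipient in 8.2.

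The core change is one sentence in a protocol amendment, with matching edits to wording. It may produce a few more IRB reports in a study of 20 subjects. The imaging procedures and the analysis are unchanged.

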8.3.2 Sponsor-Investigator reporting: Notifying the FDA

The sponsor-investigator will report to the FDA all unexpected, serious suspected adverse reactions according to the required IND Safety Reporting timelines, formats and requirements.

Unexpected fatal or life threatening suspected adverse reactions where there is evidence to suggest a causal relationship between the study drug/placebo and the adverse event, will be reported as a serious suspected adverse reaction. This will be reported to the FDA on FDA Form 3500A, no later than 7 calendar days after the sponsor-investigator's initial receipt of the information about the event.

Other unexpected serious suspected adverse reactions where there is evidence to suggest a causal relationship between the study drug/placebo and the adverse event, will be reported as a serious suspected adverse reaction. This will be reported to the FDA on FDA Form 3500A, no later than 15 calendar days after the sponsor-investigator's initial receipt of the information about the event.

Any clinically important increase in the rate of serious suspected adverse reactions over those listed in the protocol or product insert will be reported as a serious suspected adverse reaction. This will be reported to the FDA on FDA Form 3500A no later than 15 calendar days after the sponsor-investigator's initial receipt of the information about the event.

Findings from other studies in human or animals that suggest a significant risk in humans exposed to the drug will be reported. This will be reported to the FDA on FDA Form 3500A, no later than 15 calendar days after the sponsor-investigators initial receipt of the information about the event.

8.4 Stopping Rules

Stopping rules not applicable as standard radiology safety procedures will be followed.

8.5 Medical Monitoring

It is the responsibility of the Principal Investigator to oversee the safety of the study at his/her site. This safety monitoring will include careful assessment and appropriate reporting of adverse events as noted above, as well as the construction and implementation of a site data and safety-monitoring plan (see section 10 “Study Monitoring, Auditing, and Inspecting”). Medical monitoring will include a regular assessment of the number and type of serious adverse events.

8.5.1 Internal Data and Safety Monitoring

It is the responsibility of the Principal Investigator to oversee the safety of the study at his/her site. This safety monitoring will include careful assessment and appropriate reporting of adverse events as noted above, as well as the construction and implementation of a site data and safety-monitoring plan (see section 10 “Study Monitoring, Auditing, and Inspecting”). Medical monitoring will include a regular assessment of the number and type of serious adverse events.

9 Data Handling and Record Keeping

9.1 Confidentiality

Information about study subjects will be kept confidential and managed according to the requirements of the Health Insurance Portability and Accountability Act of 1996 (HIPAA). Those regulations require a signed subject authorization informing the subject of the following:

- What protected health information (PHI) will be collected from subjects in this study
- Who will have access to that information and why
- Who will use or disclose that information
- The rights of a research subject to revoke their authorization for use of their PHI.

In the event that a subject revokes authorization to collect or use PHI, the investigator, by regulation, retains the ability to use all information collected prior to the revocation of subject authorization. For subjects that have revoked authorization to collect or use PHI, attempts should be made to obtain permission to collect at least vital status (long term survival status that the subject is alive) at the end of their scheduled study period.

9.2 Source Documents

Source data is all information, original records of clinical findings, observations, or other activities in a clinical trial necessary for the reconstruction and evaluation of the trial. Source data are contained in source documents. Examples of these original documents, and data records

include: hospital records, clinical and office charts, laboratory notes, memoranda, subjects' diaries or evaluation checklists, pharmacy dispensing records, recorded data from automated instruments, copies or transcriptions certified after verification as being accurate and complete, microfiches, photographic negatives, microfilm or magnetic media, x-rays, subject files, and records kept at the pharmacy, at the laboratories, and at medico-technical departments involved in the clinical trial.

9.3 Case Report Forms

The study case report form (CRF) is the primary data collection instrument for the study. All data requested on the CRF must be recorded. All missing data must be explained. If a space on the CRF is left blank because the procedure was not done or the question was not asked, write "N/D". If the item is not applicable to the individual case, write "N/A". All entries should be printed legibly in black ink. If any entry error has been made, to correct such an error, draw a single straight line through the incorrect entry and enter the correct data above it. All such changes must be initialed and dated. Do not erase or use "white-out" for errors. For clarification of illegible or uncertain entries, print the clarification above the item, then initial and date it. If the reason for the correction is not clear or needs additional explanation, neatly include the details to justify the correction.

Data Management

Case report forms will be organized in a binder, maintained in a locked cabinet in the research coordinator's office.

Data Processing

Data will be analyzed via the statistical methods outlined in this protocol.

Data Security and Confidentiality

Patient identification codes will be used. A number will be assigned to all subjects and any published report will not identify subjects by name.

A study-specific REDCAP file will be utilized to consolidate and analyze data from the written CRFs and printed data from the EMR. The file will be a password protected within a secured folder with permissions limited to study staff. Several layers of permissions are required to access the study data. Patient-specific information will only be available on the written CRF. Only the patient number will be entered on the spreadsheet.

Data Quality Assurance

Data transcribed from the written CRFs or the EMR will be double checked by the study staff member on an ongoing basis during the study. The CRFs and EMR lab printouts will be kept in

the study binder. At the end of the study, the PI, Co-PI or a Co-investigator will again double check all data entered into the spreadsheet from the CRFs and printout EMR sheets for each subject to detect any transcription errors.

